16.0 STUDY SUSPENSION, TERMINATION, AND COMPLETION

The Sponsor may suspend or terminate the study or any part of the study at any time for any reason. If the Investigator suspends or terminates the study, the Investigator will promptly inform the Sponsor and the IRB/IEC and provide a detailed written explanation. The Investigator will also return all CB-839 test articles, containers, and other study materials to the Sponsor or designee, or destroy the materials at the investigative site. Upon study completion, the Investigator will provide the Sponsor, IRB/IEC, and regulatory agency with final reports and summaries as required by regulations.

17.0 INFORMED CONSENT

The Investigator will provide for the protection of the patients by following all applicable regulations. These regulations are available upon request from the Sponsor. The Informed Consent Form used during the informed consent process must be reviewed by the Sponsor and approved by the IRB/IEC.

Before any procedures specified in the protocol are performed, a patient must:

- Be informed of all pertinent aspects of the study and all elements of informed consent
- Be given time to ask questions and time to consider the decision to participate
- Voluntarily agree to participate in the study
- Sign and date an IRB/IEC approved Informed Consent Form

18.0 PROTOCOL AMENDMENTS

Any significant change in the study requires a protocol amendment. An Investigator must not make any changes to the study without IRB/IEC and Sponsor approval. All protocol amendments must be reviewed and approved following the same process as the original protocol.

19.0 QUALITY CONTROL AND ASSURANCE

The Sponsor or designee performs quality control and assurance checks on all clinical studies that it sponsors. Before enrolling any patients in this study, Sponsor personnel and the Investigator review the protocol, the Investigator's Brochure, the eCRFs and instructions for their completion, the procedure for obtaining informed consent, and the procedure for reporting AEs and SAEs. A qualified representative of the Sponsor will monitor the conduct of the study. During these site visits, information recorded in the eCRFs is verified against source documents.

20.0 DIRECT ACCESS, DATA HANDLING, AND RECORD KEEPING

20.1 Investigator

The Investigator will permit study-related monitoring, audits, IRB/IEC review, and regulatory inspections by providing direct access to source data and documents.

All study-related information will be recorded on source documents. All required data will be recorded in the eCRFs. All eCRF data must be submitted to the Sponsor throughout and at the end of the study.

If an Investigator retires, relocates, or otherwise withdraws from conducting the study, the Investigator must notify the Sponsor to agree upon an acceptable storage solution. Regulatory agencies will be notified with the appropriate documentation.

All study-related laboratory and clinical data gathered in this protocol will be stored in a password-protected database. All patient information will be handled using anonymous identifiers. Linkage to patients' study data is only possible after accessing a password-protected database. Access to the database is only available to individuals directly involved in the study.

Patient personal health information that is accessed for this study will not be reused or disclosed to any other person or entity, or for other research.

20.2 Sponsor

The data will be checked for completeness and correctness in real-time online.

Data are checked as they are entered into the EDC system. Off-line checks will also be run to assess the need for additional data review.

20.3 Pre-Study Documentation

The Investigator must provide the Sponsor with the following documents BEFORE enrolling any patients:

- Completed and signed form 1572
- All applicable country-specific regulatory forms
- Current, dated curricula vitae for the Investigator, Sub-Investigators, and other individuals having significant investigator responsibility who are listed on the Form 1572 or equivalent, or the clinical study information form.

- Copy of the IRB/IEC approval letter for the protocol and informed consent. All advertising, recruitment, and other written information provided to the patient must be approved by the IRB/IEC. Written assurance of continuing approval (at least annually) as well as a copy of the annual progress report submitted to the IRB/IEC must also be provided to the Sponsor.
- Copy of the IRB/IEC-approved Informed Consent Form to be used
- Where applicable, a list of the IRB/IEC members or a Federal-Wide Assurance/ Department of Health and Human Services (FWA/DHHS) number
- Copy of the protocol sign-off page signed by the Investigator
- Copy of the current medical license (online verification is also acceptable) of the Principal Investigator, any Sub-Investigators and any other individuals having significant responsibility as listed in the 1572
- Fully executed Clinical Trial Agreement (CTA)
- Financial disclosure form for the Principal Investigator and any other persons listed in the 1572
- A written document containing the name, location, certification number, and date of certification of the laboratory to be used for laboratory assays and those of other facilities conducting tests. This document should be returned along with the 1572. The Sponsor must be notified if the laboratory is changed or if any additional laboratory is to be used.

20.4 Records Retention

The Investigator shall retain and preserve one copy of all data generated in the course of the study, specifically including but not limited to those defined by GCP as essential, for the longer of: (i) 2 years after the last marketing authorization for the study drug has been approved or the Sponsor has discontinued its research with respect to such drug or (ii) such longer period as required by applicable global regulatory requirements. At the end of such period, the Investigator shall notify the Sponsor in writing of its intent to destroy all such material. The Sponsor shall have 30 days to respond to the Investigator's notice, and the Sponsor shall have a further opportunity to retain such materials at the Sponsor's expense.

21.0 AUTHORSHIP AND ACCOUNTABILITY

Per the International Committee of Medical Journal Editors (ICMJE) recommendations, an author is generally considered to be anyone who provides substantive intellectual contributions to a published study. Specifically, authorship credit should be based on 1) substantial contributions to study conception and design, or acquisition, analysis and interpretation of data, and 2) drafting the article or revising it critically for important intellectual content, 3) final approval of the version to be published, and 4) agreement to be accountable for all aspects of the work to ensure its accuracy and integrity. All four conditions should be met.

22.0 LIST OF ABBREVIATIONS

Abbreviation or Term¹	Definition/Explanation
AE	Adverse event
ALT	Alanine aminotransferase
ANC	Absolute Neutrophil Count
aPTT	Activated partial thromboplastin time
AST	Aspartate aminotransferase
BID	Twice daily
CBE	CB-839 plus everolimus combination treatment
C _{cr}	Creatinine Clearance
ccRCC	Clear Cell Renal Cell Carcinoma
CFR	Code of Federal Regulations
CI	Confidence interval
cm	Centimeters
C _{max}	Maximum observed concentration
CNS	Central nervous system
CR	Complete remission
CTA	Clinical Trial Agreement
CT	Computed tomography
CTCAE	Common Terminology Criteria for Adverse Events
CV	Coefficient of variation
CYP, CYP450	Cytochrome P450
DCR	Disease Control Rate
DICOM	Digital Imaging and Communications in Medicine
DLT	Dose Limiting Toxicity
DOR	Duration of Response
ECG	Electrocardiogram
eCRF	Electronic Case Report Form
EDC	Electronic data capture
EOT	End of Treatment
FDA	Food and Drug Administration
GCP	Good Clinical Practice
g/dL	Grams per deciliter
GLP	Good Laboratory Practice
GMP	Good Manufacturing Practice
Hb	Hemoglobin
HbA1C	Glycated Hemoglobin
HIV	Human immunodeficiency virus
HR	Heart rate

Abbreviation or Term¹	Definition/Explanation
hr	Hour or hours
ibid	The same reference as above
IC ₅₀	Half maximal inhibitory concentration
ICF	Informed Consent Form
IEC	Independent Ethics Committee
IMDC	International Metastatic Renal Cell Carcinoma Database
INR	International Normalized Ratio
IRB	Institutional Review Board
IV	Intravenous, intravenously
kg	Kilogram
KPS	Karnofsky Performance Score
LDH	Lactate dehydrogenase
LFT	Liver Function Test
LC-MS/MS	Liquid chromatography-mass spectrometry/mass spectrometry
mcL/ µL	Microliter
MedDRA	Medical Dictionary for Drug Regulatory Activities
mg	Miligram
mL	Milliliter
mo	Months
MOA	Mechanism of Action
mRCC	Metastatic Renal Cell Carcinoma
MRI	Magnetic Resonance Imaging
MSKCC	Memorial Sloan Kettering Cancer Center
MTD	Maximum tolerated dose
mTOR	Mechanistic Target of Rapamycin
NHL	Non-Hodgkin's Lymphoma
NSCLC	Non-Small Cell Lung Cancer
ORR	Overall response rate
OS	Overall Survival
PboE	Placebo tablets plus everolimus treatment
PD-1	Programmed Cell Death protein 1
PD-L1	Programmed Death Ligand 1
PgP	P-Glycoprotein
PFS	Progression Free Survival
PK	Pharmacokinetic(s)
PO	Per os (administered by mouth)
PPI	Proton Pump Inhibitors
PR	Partial response

Abbreviation or Term¹	Definition/Explanation
PSA	Prostate Specific Antigen
PT	Prothrombin time
QD	Once-daily dosing
QTcF	Corrected QT interval, Fridericia's formula
RP2D	Recommended Phase 2 Dose
RBC	Red Blood Cell
RCC	Renal cell carcinoma
RECIST	Response Evaluation Criteria in Solid Tumors
SAE	Serious adverse event
Scr	Serum Creatinine
SD	Stable disease
TKI	Tyrosine Kinase Inhibitor
T _{max}	Time of maximum observed concentration
TEAE	Treatment-emergent adverse event
TID	Three times daily
TNBC	Triple negative breast cancer
ULN	Upper limit of normal
VEGF	Vascular Endothelial Growth Factor

- ¹ This may not be a comprehensive list of all abbreviations in this document. All of these abbreviations may or may not be used in this document.

ATTACHMENT 1: SCHEDULE OF STUDY ASSESSMENTS

(1 cycle = 28 days)	Pre-randomization	Post-randomization				
	Screening ¹	Cycle 1		Cycle 2+	Cycle 13+ (Every 3 cycles) ¹³	End of Treatment/ Follow up
Assessments	≤ 21 days prior to CID1	Day 1 ² (≤3 days post randomization)	Day 15 (± 2 days)	Day 1 (± 5 days)	Day 1 (± 7 days)	EOT: Within 28 days post treatment discontinuation
Written Informed Consent	X					
Inclusion/Exclusion Criteria	X					
Demographics and Medical History	X					
Physical Examination ³	X	X	X	X	X	X
Height	X					
Weight	X	X	X	X	X	X
Vital Signs ⁴	X	X	X	X	X	X
Karnofsky Performance Status	X	X		X	X	X
12-lead ECG with QTcF	X					
Urinalysis ⁵	X					
HgA1c levels ^{5, 6}	X					
Triglyceride and total cholesterol levels ^{5, 7}	X			X		
Coagulation tests ⁵	X					
Serum Chemistry levels	X	X	X	X	X	X
Hematology	X	X	X	X	X	X
Serum or Urine Pregnancy Test ⁸	X					X
Pharmacokinetic (PK) Assay ⁹			X	X		
CB-839 or Placebo Dosing		CB-839 or Placebo will be administered twice daily (BID) with food				
Everolimus Dosing		Everolimus will be administered once daily (QD) at the same time every day.				
Optional Tumor Biopsy		Can be collected any time on study. Patients must sign the optional tumor biopsy consent				
Archival Tumor Collection	X					

(1 cycle = 28 days)	Pre-randomization	Post-randomization				
Visit	Screening ¹	Cycle 1		Cycle 2+	Cycle 13+ (Every 3 cycles) ¹³	End of Treatment/ Follow up
Assessments	≤ 21 days prior to C1D1	Day 1 ² (≤3 days post randomization)	Day 15 (± 2 days)	Day 1 (± 5 days)	Day 1 (± 7 days)	EOT: Within 28 days post treatment discontinuation
Radiographic Evaluation of Tumor Burden (diagnostic CT with intravenous contrast or MRI) ¹⁰	X ¹¹			Every 8 weeks	Every 12 weeks	X
Quality of Life Questionnaires		X		X	X	X
Adverse Events		Document new or worsening AEs from time of first dose through 28 days after study treatment discontinuation. AE information will be collected at study visits and may also be collected via any other forms of communication or by subject report. Certain AEs and SAEs that are ongoing 28 days after study discontinuation are to be followed until resolution or determination by the investigator that the event is stable or irreversible.				
Concomitant Medications	Document concomitant medication taken from time of informed consent through 28 days after study treatment discontinuation.					
Follow up						X ¹²

Explanation of Superscripts

1. Results of screening assessments must be reviewed before randomization to confirm that the patient meets all eligibility criteria. An IRB/IEC-approved Informed Consent Form (ICF) must be signed and dated ≤42 days prior to C1D1.
2. Assessments on C1D1 should be completed prior to first dose of study treatment unless otherwise indicated.
3. Complete physical exam is required at Screening and at End of Treatment. A symptom-directed physical exam can be done on all other visits. System exams are only required as clinically indicated
4. Vital sign measurements include temperature, pulse, respiratory rate and resting systolic and diastolic blood pressure.
5. Assessment completed at screening. Investigators should monitor during the study if it is deemed necessary per everolimus Package Insert
6. Investigators should periodically monitor fasting glucose as per everolimus Package Insert.
7. Triglycerides should be repeated at Cycle 2 (+/-5days). Total cholesterol levels are required at baseline only.
8. Required for all females of child-bearing potential. Screening pregnancy test must occur within 3 days prior to C1D1.
9. Samples are collected on C1D15: pre-dose and 2 hrs post dose and on C2D1: 4 hrs and 6 hrs post dose. Refer to the laboratory manual for detailed instructions on samples kits, collection, and shipment to a central laboratory.
10. Imaging should be done at the same institution/facility and with the same modality which will be used to measure response during the patient’s participation in the study.
11. Tumor assessments within 28 days prior to C1D1 will be accepted.
12. Patients will be contacted every 3 mo for the first 12 mo then every 6 mo thereafter to confirm survival.
13. Starting with Cycle 13, assessments will be completed every 3 cycles (12 weeks). More frequent visits should be completed if clinically indicated.

ATTACHMENT 2: CLINICAL LABORATORY TESTS**Hematology (Peripheral Blood Sample):**

- Hemoglobin
- Hematocrit
- Red blood cell count
- White blood cell count with differential
- Platelet count

Coagulation Tests

- PT, aPTT and INR

Serum Chemistry-Full Metabolic Panel (Peripheral Blood Sample) with additional analytes

- | | |
|-----------------------|---|
| • Sodium | • Total protein |
| • Potassium | • Albumin |
| • Chloride | • Total and direct bilirubin ¹ |
| • CO ₂ | • Aspartate aminotransferase (AST) |
| • Calcium | • Alanine aminotransferase (ALT) |
| • Glucose | • Alkaline phosphatase (AP) |
| • Blood urea nitrogen | • Lactate dehydrogenase (LDH) |
| | • Creatinine |

¹ Direct bilirubin is only required if Total Bilirubin is above the upper limit of normal.

Pregnancy test (urine or serum β -HCG): Women of child-bearing potential**Urinalysis**

- | | |
|--------------|---|
| • Protein | • Leukocyte esterase |
| • Glucose | • pH |
| • Ketones | • Specific gravity |
| • Hemoglobin | • Urobilinogen |
| • Nitrite | • Microscopic evaluation(performed at the discretion of the Investigator based on results of routine urinalysis or as clinically indicated) |

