Table 9.5-2: CB-839 Related Adverse Events in $\geq 5\%$ of Patients Treated with Monotherapy CB-839 on the BID Schedule on Study CX-839-001
BID Schedule - Monotherapy (N=88): CB-839 Related TEAEs

MedDRA Preferred Term	Number (%) of patients	
	All Events	\geq Grade 3 [^]
Patients with Any CB-839-Related TEAE	61 (69.3)	3 (3.4)
FATIGUE	21 (23.9)	0
NAUSEA	20 (22.7)	0
ALANINE AMINOTRANSFERASE INCREASED	13 (14.8)	2 (2.3)
PHOTOPHOBIA	12 (13.6)	0
ASPARTATE AMINOTRANSFERASE INCREASED	10 (11.4)	1 (1.1)
DECREASED APPETITE	7 (8.0)	0
GAMMA-GLUTAMYLTRANSFERASE INCREASED	7 (8.0)	2 (2.3)
BLOOD ALKALINE PHOSPHATASE INCREASED	6 (6.8)	1 (1.1)
VOMITING	5 (5.7)	0

[^]no Grade 4 or Grade 5 events

Photophobia and related ocular toxicities (e.g., photopsia) have been identified as CB-839-related events. In all but one case, these events have been Grade 1 and without impact on patients' daily lives. One photophobia event was characterized as Grade 2 and required the patient rest for 1-2 hr in a dark room. These events appear to occur around C_{max} (1-4 hr after dosing) and resolve with time. Anecdotal reports suggest that these events tend to become less frequent over extended dosing. The AE profile of monotherapy CB-839 using the original schedule (TID without food) as well as the final schedule (BID with food) are described more completely in the Investigator's Brochure.

CB-839 + Everolimus

The combination of CB-839 with everolimus has been well tolerated to date. The frequency of adverse events (reported as of the safety data cut of 23 January 2017) in patients receiving CB-839 on the BID regimen in combination with standard dose everolimus (10 mg QD orally) are provided in [Table 9.5-3](#) (all adverse events) and [Table 9.5-4](#) (treatment related adverse events). Of the first 19 patients who have received escalating doses of CB-839 (7 at 400 mg, 9 at 600 mg and 3 at 800 mg orally BID with food) in combination with everolimus, the most frequent AEs were anemia, decreased appetite, creatinine increase and hyperglycemia; with anemia,

hyperglycemia and fatigue being the most frequent Grade 3/4 AEs. Of note, both patients with G3 hyperglycemia had preexisting diabetes (Table 9.5-3).

Table 9.5-3: Adverse Events in ≥ 3 Patients Treated with CB-839 + Everolimus on Study CX-839-001

CB-839 + Everolimus (N=19): All TEAEs		
MedDRA Preferred Term	Number (%) of patients	
	All Events	\geq Grade 3
Patients with Any TEAE in CBE Cohort	19 (100.0)	13 (68.4)

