ANAEMIA	13 (68.4)	5 (26.3)
DECREASED APPETITE	9 (47.4)	0
BLOOD CREATININE INCREASED	7 (36.8)	0
HYPERGLYCAEMIA	7 (36.8)	2 (10.5)*
COUGH	6 (31.6)	0
NAUSEA	6 (31.6)	0
DIARRHOEA	5 (26.3)	1 (5.3)
HEADACHE	5 (26.3)	1 (5.3)
PROTEINURIA	5 (26.3)	0
VOMITING	5 (26.3)	0
ASPARTATE AMINOTRANSFERASE INCREASED	4 (21.1)	0
FATIGUE	4 (21.1)	2 (10.5)
STOMATITIS	4 (21.1)	0
ABDOMINAL PAIN	3 (15.8)	1 (5.3)
ALANINE AMINOTRANSFERASE INCREASED	3 (15.8)	0
CHILLS	3 (15.8)	0
DERMATITIS ACNEIFORM	3 (15.8)	0
DYSGEUSIA	3 (15.8)	0
DYSPNOEA	3 (15.8)	0
HYPOMAGNESAEMIA	3 (15.8)	0
HYPOPHOSPHATAEMIA	3 (15.8)	1 (5.3)
INSOMNIA	3 (15.8)	0
MUCOSAL INFLAMMATION	3 (15.8)	0
MYALGIA	3 (15.8)	1 (5.3)
PAIN	3 (15.8)	1 (5.3)
PLATELET COUNT DECREASED	3 (15.8)	0
PYREXIA	3 (15.8)	0
THROMBOCYTOPENIA	3 (15.8)	0
WEIGHT DECREASED	3 (15.8)	0

*preexisting diabetes

Treatment-related adverse events that were Grade 3 were few in number and there have been no Grade 4 events (Table 9.5-4). One event of Grade 3 rash occurred at the 400 mg BID dose level, which was considered a dose limiting toxicity (DLT). The rash was considered related to everolimus and resolved upon a dose reduction of everolimus (CB-839 continued at full dose). No additional DLTs have been reported in subsequent patients treated at 400, 600 or 800 mg BID and a maximum tolerated dose has not been identified.

Table 9.5-4: Treatment-Related Adverse Events in ≥ 3 Patients Treated with CB-839 + Everolimus on Study CX-839-001

CB-839 + Everolimus (N=19): Treatment-related TEAEs*		
MedDRA Preferred Term	Number (%) of patients	
	All Events	\geq Grade 3[^]
Patients with Any Treatment-related TEAE in CBE cohort	19 (100)	9 (47.4)
DECREASED APPETITE	7 (36.8)	0
ANAEMIA	5 (26.3)	1 (5.3)
DIARRHOEA	5 (26.3)	0
HYPERGLYCAEMIA	5 (26.3)	2 (10.5)
PROTEINURIA	5 (26.3)	0
ASPARTATE AMINOTRANSFERASE INCREASED	4 (21.1)	0
BLOOD CREATININE INCREASED	4 (21.1)	0
FATIGUE	4 (21.1)	2 (10.5)
NAUSEA	4 (21.1)	0
STOMATITIS	4 (21.1)	0
ALANINE AMINOTRANSFERASE INCREASED	3 (15.8)	0
DERMATITIS ACNEIFORM	3 (15.8)	0
DYSGEUSIA	3 (15.8)	0
MUCOSAL INFLAMMATION	3 (15.8)	0
MYALGIA	3 (15.8)	0
THROMBOCYTOPENIA	3 (15.8)	0
VOMITING	3 (15.8)	0

[^]no Grade 4 or Grade 5 events

*considered to be at least possibly related to either CB-839 or everolimus

Please refer to the most recent CB-839 Investigator's Brochure for additional safety information from the Phase 1 studies.

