10.6.5 Laboratory Assessments

Laboratory evaluations will be performed as noted in the Schedule of Study Assessment ([Attachment 1](#)). The laboratory analytes are listed in [Attachment 2](#). All laboratory assessments will be completed by the sites local laboratory and results entered in the EDC.

To confirm eligibility, urinalysis, coagulation, HbA1c, and triglycerides, and total cholesterol will be performed at screening. These assessments should be repeated periodically during the course of the study as clinically indicated. Any clinically significant results should be entered in the EDC.

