14.4 Safety Analysis

Safety will be assessed by the incidence and severity of adverse events (AEs); the analysis will be performed on the Safety Analysis Patient Set as defined in [Section 14.4.2](#).

Adverse events will be coded by System Organ Class (SOC) and Preferred Term (PT) using the Medical Dictionary for Regulatory Activities (MedDRA). The number and proportion of patients reporting a given AE will be tabulated by treatment group according to the worst severity reported. Separate tables will be constructed for a) all reported AE's, b) serious AEs (SAEs), and c) AE's leading to permanent discontinuation of study treatment. The above tables will also be presented for treatment-emergent AEs (TEAEs) judged to be related to the study treatment.

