15.1 Definitions

An **adverse event** (AE) is any untoward, undesired, or unplanned event in the form of signs, symptoms, disease, or laboratory or physiologic observations occurring in a person given a test article or associated with other protocol interventions in a clinical study. The event does not need to be causally related to the test article. An AE includes, but is not limited to, the following:

- Any AE not previously observed in the patient that emerges during the protocol specified AE reporting period
- Any clinically significant worsening of a preexisting condition
- Complications occurring as a result of protocol-mandated interventions (e.g., invasive procedure such as biopsies), including in the period prior to receiving the first dose of

the test article that are related to the protocol-mandated intervention (e.g., medication wash out, biopsies)

- An AE occurring from overdose (i.e., a dose higher than that indicated in the protocol) of a test article, whether accidental or intentional
- An AE occurring from abuse (e.g., use for nonclinical reasons) of a test article
- An AE that has been associated with the discontinuation of the use of a test article

Any treatment-emergent abnormal laboratory result which is clinically significant, i.e., meeting one or more of the following conditions, should be recorded as a single diagnosis on the adverse event page in the eCRF:

- Accompanied by clinical symptoms
- Leading to a change in study medication (e.g., dose modification, interruption, or permanent discontinuation)
- Requiring a change in concomitant therapy (e.g., addition of, interruption of, discontinuation of, or any other change in a concomitant medication, therapy or treatment)

A **serious adverse event** (SAE) is an AE that:

- Results in death (NOTE: death is an outcome, not an event)
- Is life-threatening (NOTE: see definition below)
- Requires inpatient hospitalization or prolongation of an existing hospitalization
- Results in a persistent or significant disability or incapacity
- Results in a congenital anomaly or birth defect
- Additionally, important medical events that may not result in death, be life-threatening, or require hospitalization may be considered SAEs when, based on appropriate medical judgment, they may jeopardize the patient and may require medical or surgical intervention to prevent one of the outcomes listed in this definition. Examples of such events include allergic bronchospasm requiring

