### **8.6.3 Laboratory Data**

Laboratory data will be summarized by treatment arm. Values outside the normal ranges will be summarized by treatment arm. In addition, selected laboratory data will be summarized by treatment arm and NCI CTCAE v4.3 grade.

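### The scheduled chemistry panel leaves out GGT, magnesium and phosphate, all reported as adverse events in Phase 1; adding them is a cheap way to make their by-arm comparison systematic

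*Protocol*

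**What the plan says.** Protocol 10.6.5 refers to Attachment 2 for the analytes and has all tests run at site laboratories. Attachment 2, under "Serum Chemistry-Full Metabolic Panel (Peripheral Blood Sample) with additional analytes", names sodium, potassium, chloride, CO2, calcium, glucose, blood urea nitrogen, total protein, albumin, bilirubin, AST, ALT, alkaline phosphatase, LDH and creatinine. Attachment 1 schedules that panel at Screening, C1D1, C1D15, Day 1 of later cycles (every third cycle from Cycle 13) and End of Treatment. Neither Attachment 1 with its footnotes nor SAP Appendix B adds an analyte.

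Protocol 9.5 gives the Phase 1 experience. Table 9.5-2 (CB-839-related events, monotherapy, N=88) has a row for "GAMMA-GLUTAMYLTRANSFERASE INCREASED". Table 9.5-3 (all treatment-emergent events, CB-839 + everolimus, N=19) has rows for "HYPOPHOSPHATAEMIA" and "HYPOMAGNESAEMIA".

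On analysis, SAP 6.1.3 makes change in clinical laboratory results a safety endpoint. SAP 8.6.3 says "Laboratory data will be summarized by treatment arm", and adds CTCAE grade tables for selected laboratory data that it does not name. Protocol 14.4 covers adverse events: "The number and proportion of patients reporting a given AE will be tabulated by treatment group according to the worst severity reported".

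**The concern.** Comparing the safety of CBE and PboE is one of the additional objectives in Protocol 5.0. Everolimus is given in both arms, so the placebo control can show what CB-839 adds, which an uncontrolled Phase 1 cohort could not. For these three analytes that advantage is largely lost, because nothing requires a value to exist in either arm, at baseline or on treatment.

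The adverse event route only partly fills the gap. Protocol 15.1 sends to the adverse event page "Any treatment-emergent abnormal laboratory result which is clinically significant, i.e., meeting one or more of the following conditions": symptoms, a change in study medication, or a change in concomitant therapy. Each condition presupposes a result. Protocol 9.5 describes the Grade 3/4 liver function elevations seen on the BID schedule as asymptomatic, so testing prompted by symptoms is a weak way to find changes of that kind.

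**Working it through.** **1. Is any of the three on the panel?** Checking the 15 listed analytes (total and direct bilirubin counted as one) against GGT, magnesium and phosphate gives 0 of 3. Scheduled measurements under the current plan: none.

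**2. Reproduce the Phase 1 figures** (rate = n/N; exact Clopper-Pearson 95% CI).

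| Term | Source | Any grade | Grade 3 or higher |
|---|---|---|---|
| GGT increased | Table 9.5-2, related, monotherapy | 7/88 = 8.0% (CI 3.3 to 15.7%) | 2/88 = 2.3% (CI 0.3 to 8.0%) |
| Hypophosphataemia | Table 9.5-3, all-causality, combination | 3/19 = 15.8% (CI 3.4 to 39.6%) | 1/19 = 5.3% (CI 0.1 to 26.0%) |
| Hypomagnesaemia | Table 9.5-3, all-causality, combination | 3/19 = 15.8% (CI 3.4 to 39.6%) | 0/19 = 0% (CI 0 to 17.6%) |

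The point estimates match the tables.

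**3. Expected patients in the CBE arm.** Protocol 14.5 plans 42 experimental and 21 control patients. Expected count = 42 × Phase 1 rate.
- GGT, any grade: 42 × 7/88 = 3.3; range 42 × 0.033 = 1.4 to 42 × 0.157 = 6.6.
- Phosphate and magnesium, any grade, each: 42 × 3/19 = 6.6; range 42 × 0.034 = 1.4 to 42 × 0.396 = 16.6.
- Grade 3 or higher: GGT 42 × 2/88 = 1.0; phosphate 42 × 1/19 = 2.2.

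**4. How much does GGT add to the liver tests already scheduled?** Table 9.5-2 has 2 patients with related Grade 3 or higher GGT, 2 with related Grade 3 or higher ALT, and 3 with any related event at that grade. Since 2 + 2 − 3 = 1, at least one patient had both. So at most 1 of 88 had related Grade 3 or higher GGT without ALT at that grade.

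**5. Does the absence of GGT from the combination tables count against it?** Tables 9.5-3 and 9.5-4 list only terms seen in 3 or more patients. At the monotherapy rate, 19 × 7/88 = 1.5 patients would be expected, below the cut-off. The absence is uninformative.

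**The case against.** The strongest reply is that panel breadth in a 63-patient Phase 2 trial is a design choice, and nothing in the documents contradicts it. Safety is an additional objective, and SAP 8.6.3 promises grade tables only for selected analytes. Several parts of this reply stand.

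- A reader might infer that the three events cannot be compared by arm at all. The documents do not support that: Protocol 14.4 and SAP 8.6.2 tabulate adverse event terms by arm and grade. What is lost is unselected ascertainment.
- A reader might infer bias between arms from site testing habits. The trial is randomised and double-blind, which limits differential testing. The main consequence is under-counting.
- A reader might take all three as drug toxicities reaching Grade 3. Hypomagnesaemia had no such case. Only GGT is shown as CB-839-related, and that on monotherapy. Neither electrolyte term appears in treatment-related Table 9.5-4, although its 3-patient cut-off leaves one or two related cases possible.
- Liver safety is not unmonitored. ALT, AST, alkaline phosphatase and bilirubin are drawn at every chemistry visit, and step 4 shows the overlap with GGT at Grade 3 or higher.
- Starting a replacement drug counts as a change in concomitant therapy under Protocol 15.1, so a treated electrolyte abnormality would be recorded. Protocol 10.3 and 10.6 also allow extra safety evaluations when clinically indicated.

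The reply does not supply the missing values. Blinding gives no baseline and no denominator, and a change that is asymptomatic, untreated and leads to no study-drug change would not be recorded.

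**Conclusion.** The point holds as a cheap improvement, not as an error that invalidates an analysis. The primary PFS analysis is unaffected. For GGT, magnesium and phosphate, the laboratory-change endpoint in SAP 6.1.3 and the summaries in SAP 8.6.3 cannot be delivered systematically, and adverse event counts are likely to be low.

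The expected counts in step 3 assume that Phase 1 rates carry over. That is uncertain: only 3 of the 19 combination patients received 800 mg BID, the GGT rate comes from monotherapy, and the documents do not say how these analytes were tested in Phase 1. With 21 controls, any by-arm contrast would be imprecise and descriptive even with complete measurement. The gain is complete, unselected data rather than a powered comparison.

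**What to change.** Add GGT, magnesium and phosphate to the serum chemistry list in Protocol Attachment 2, at the time points already scheduled for chemistry in Attachment 1. Name them among the selected analytes in SAP 8.6.3, so that they enter the by-arm summaries and CTCAE grade tables.

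If the sponsor keeps the panel as it is, or for patients already enrolled without a baseline, the SAP should state that these events come from unscheduled testing and adverse event reports only and are probably under-counted.

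The cost is three more assays on blood already drawn and run locally, plus eCRF fields and some data entry. No visit is added.
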